8.2. Subject Disposition and Population Assignment

Subject disposition and population assignment will be listed.

A summary table by treatment will be provided, based on the safety population.

8.3. Screening Demographics and Baseline Characteristics

The screening demographics and baseline characteristics including age, sex, race, ethnicity, height, body weight, and body mass index will be listed.

A summary table by treatment will be provided, based on the safety population.

8.4. Prior and Concomitant Medication

Prior medication will be defined as medication that starts within 30 days prior to enrollment and ends prior to dosing. Concomitant medication will be defined as medication that starts during or after dosing or starts but does not end prior to dosing.

Prior and concomitant medications will be coded using the World Health Organization Drug Dictionary (WHODrug) Global, Format B3, Version September 2020 (or later if a new version is issued during the study; see the data management plan [DMP] for more details). Prior and concomitant medications will be listed.

8.5. Pharmacokinetic Assessments

8.5.1. Pharmacokinetic Analysis

The following PK parameters will be determined where possible from the plasma concentrations of rosuvastatin on Days 1 and 6 and sotorasib on Day 6 using noncompartmental methods in validated software program Phoenix WinNonlin (Certara, Version 8.1 or higher):

Parameter	Units ^a	Definition
AUC _{last}	h*ng/mL	area under the plasma concentration-time curve from time zero to the last quantifiable concentration ^b
$\mathrm{AUC}_{\mathrm{inf}}$	h*ng/mL	area under the plasma concentration-time curve from time zero extrapolated to infinity ^b , ^c
C_{max}	ng/mL	maximum observed plasma concentration
t_{max}	h	time of the maximum observed plasma concentration
t_{last}	h	time of the last quantifiable plasma concentration
$t_{1/2}$	h	apparent terminal elimination half-life
CL/F	L/h	apparent total clearance
V_z/F	L	apparent volume of distribution during the terminal phase

^a Units are based on concentration units (provided by the bioanalytical lab or preferred units for presentation of PK parameters) and dose units used in the study.

Additional PK parameters may be determined where appropriate.

^b The AUC will be calculated using the linear trapezoidal rule.

^c Based on the last observed quantifiable concentration

Pharmacokinetic analysis will be carried out where possible using actual dose administered (mg) and actual postdose blood sampling times. If an actual time is missing, nominal times may be used with sponsor's approval.

Concentrations are used as supplied by the analytical laboratory for PK analysis. The units of concentration and resulting PK parameters, with amount or concentration in the unit, will be presented as they are received from the analytical laboratory.

The parameters C_{max}, t_{last}, and t_{max} will be obtained directly from the concentration-time profiles.

For multiple peaks, the highest postdose concentration will be reported as C_{max} . In the case that multiple peaks are of equal magnitude, the earliest t_{max} will be reported.

8.5.1.1. Criteria for the Calculation of Apparent Terminal Elimination Rate Constant and Half-life

The start of the terminal elimination phase for each subject will be defined by visual inspection and generally will be the first point at which there is no systematic deviation from the log-linear decline in concentrations.

The apparent terminal elimination rate constant (λ_z) will only be calculated when a reliable estimate can be obtained using at least 3 data points, preferably not including C_{max}, and the adjusted coefficient for determination of exponential fit (\mathbb{R}^2 -adj) of the regression line is ≥ 0.8 . Parameters requiring λ_z for their calculation (eg, AUC_{inf}, $t_{1/2}$, CL/F, V_z /F) will only be calculated if the R^2 -adj value of the regression line is >0.8.

The following regression-related diagnostic PK parameters will be determined, when possible:

Parameter	Units	Definition
λ_z	1/h	apparent terminal elimination rate constant
λ_z Upper	h	end of exponential fit
λ_z Lower	h	start of exponential fit
$\lambda_z N$	NA	number of data points included in the log-linear regression
λ_z Span Ratio	NA	time period over which λ_z was determined as a ratio of $t_{1/2}$
%AUC _{extrap}	%	percentage of area under the concentration-time curve due to extrapolation from the last quantifiable concentration to infinity
R ² -adj	NA	adjusted coefficient for determination of exponential fit

Where possible, the span of time used in the determination of λ_z (ie, the difference between λ_z Upper and λ_z Lower) should be ≥ 2 half-lives. If the λ_z Span Ratio is ≤ 2 , the robustness of the $t_{1/2}$ values will be discussed in the clinical study report (CSR).

CONFIDENTIAL

8.5.1.2. Criteria for Calculation and Reporting of Area Under the Concentration-time Curve

The minimum requirement for the calculation of AUC will be the inclusion of at least 3 consecutive concentrations above the lower limit of quantification. If there are only 3 consecutive concentrations, at least 1 should follow C_{max} .

If the extrapolated area is >20%, AUC_{inf} (and derived parameters) will be flagged and may be excluded from the summary statistics and statistical analysis at the discretion of the sponsor or pharmacokineticist.

If AUC_{inf} cannot be determined reliably for all subjects and/or treatments, an alternative AUC measure, such as AUC to a fixed timepoint may be included in the statistical analysis upon sponsor approval.

8.5.1.3. Criteria for Handling Below the Limit of Quantification or Missing Concentrations for Pharmacokinetic Analysis

Plasma concentrations below the limit of quantification (BLQ) will be assigned a value of 0 before the first measurable concentration and thereafter BLQ concentrations will be treated as missing. The following rules apply to the specific situations defined below:

- If an entire concentration-time profile is BLQ, it will be excluded from PK analysis.
- Where 2 or more consecutive concentrations are BLQ at the end of a profile, the profile will be deemed to have terminated and any further quantifiable concentrations will be set to missing for the calculation of the PK parameters, unless they are considered to be a true characteristic of the profile of the drug.
- If a predose plasma concentration is missing, it will be set to 0 by default within Phoenix WinNonlin.

8.5.1.4. Treatment of Outliers in Pharmacokinetic Analysis

If a value is considered to be anomalous due to being inconsistent with the expected PK profile, it may be appropriate to exclude the value from the PK analysis. However, the exclusion of any data must have strong justification and will be documented in the CSR.

Any quantifiable predose concentration value will be considered anomalous for rosuvastatin on Day 1 and will be set to missing for the PK analysis. This will be set to 0 by default in Phoenix WinNonlin.

If the predose concentration is >5% of C_{max} in the second treatment period for rosuvastatin, all PK concentration and parameter data will be excluded from the summary statistics and statistical analysis for that period.

8.5.2. Presentation of Pharmacokinetic Data

If the actual time of sample collection deviates from the nominal time by more than $\pm 10\%$, the plasma concentration will be flagged and excluded from the summary statistics.

Individual concentrations deemed to be anomalous will be flagged in the listings and excluded from the summary statistics.

For plasma concentration data the following rules will apply:

- Values that are BLQ will be set to 0 for the calculation of summary statistics.
- If the embedded BLQ value is considered anomalous within the concentration-time profile, this value will be excluded from the summary statistics.
- Where there is NR, these will be set to missing.
- If there are less than three values in the data series, only the min, max and N will be presented. The other summary statistics will be denoted as not calculated (NC). BLQ is considered a value.
- If the values are BLQ, then the arithmetic mean, arithmetic SD, median, min and max will be presented as zero, 0 and the geometric mean and geometric coefficient of variation (CV%) will be denoted as NC.
- Arithmetic mean or median values that are BLQ will be presented as 0, and the geometric mean and geometric CV% will be denoted as NC.

For PK parameters the following rule will apply:

- For the calculation of summary statistics of PK parameters, all non-reportable and NC values in a data series will be set to missing.
- AUC_{inf} and AUC_{last} will be set to NC if they were calculated using fewer than three concentrations, and/or three concentrations if the last is C_{max}.
- Geometric mean and coefficient of variation will not be calculated for t_{last} or t_{max} .

8.5.3. Pharmacokinetic Statistical Methodology

All PK concentrations and parameters will be listed.

Summary tables, mean (+ standard deviation [SD]) figures, overlaying individual figures, and individual figures by treatment and time postdose will be provided for plasma PK concentrations. All figures will be produced on both linear and semi-logarithmic scales.

Summary tables by treatment will be provided for all PK parameters, with the exception of regression-related PK parameters.

A statistical analysis will be conducted to investigate the drug-drug interaction on the PK of rosuvastatin by comparing 960 mg sotorasib + 10 mg rosuvastatin (test treatment) to 10 mg rosuvastatin (reference treatment) for AUC_{last}, AUC_{inf}, and C_{max}.

The natural log (ln)-transformed PK parameters will be analyzed using a mixed model. The model will include treatment as fixed effect and subject as a random effect.

For AUC_{last}, AUC_{inf}, and C_{max} separately, the least squares mean (LSM) for each treatment, difference in LSMs between the test and reference treatments, and corresponding 90% confidence interval (CI) will be calculated; these values will then be back-transformed to give the geometric least square mean (GLSM), ratio of GLSMs, and corresponding 90% CI.

Additionally, the pooled estimate (across all treatments) of the within-subject CV will be calculated, and residual plots will be produced to assess the adequacy of the model(s) fitted.

Examples of the SAS code that will be used are as follows:

Mixed Model Analysis

```
proc mixed data = <data in>;
  by parcatln parcatl pkday paramn param;
  class trtan usubjid;
  model ln pk = trtan / cl residual ddfm = kr;
  lsmeans trtan / cl pdiff = control('1') alpha = 0.1;
  random usubjid;
  ods output lsmeans = <data out>;
  ods output diffs = <data out>;
  ods output covparms = <data out>;
```

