5.6. Randomization

This is a nonrandomized study. The study has a fixed treatment sequence.

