8.3. Pharmacokinetic Analyses

The plasma PK parameters of rosuvastatin on Days 1 and 6, and sotorasib on Day 6 will be calculated using standard noncompartmental methods.

The primary PK parameters are C_{max} , AUC_{last} , and AUC_{inf} for rosuvastatin on Days 1 and 6. All other PK parameters will be regarded as secondary and will not be subject to inferential statistical analysis. A linear mixed-effects model will be used to analyze log-transformed primary PK parameters. The model assumes fixed effect for treatment and a random effect for subject. Geometric mean ratios for C_{max} and AUC values and associated 90% confidence intervals (test/reference) will be estimated. The “reference” treatment for PK analysis will be rosuvastatin administered alone, while the “test” treatment will be rosuvastatin administered in combination with sotorasib.

Additional parameters may be calculated. Specific details will be presented in the Statistical Analysis Plan for this study.

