1. INTRODUCTION

This SAP has been developed after review of the clinical study protocol (Final Version 1.0 dated 19 May 2021) and electronic case report form (eCRF).

This SAP describes the planned analysis of the pharmacokinetic (PK), safety, and tolerability data from this study. A detailed description of the planned TFLs to be presented in the clinical study report (CSR) is provided in the accompanying TFL shells document.

In general, the analyses are based on information from the protocol, unless they have been modified by agreement with Amgen Inc. A limited amount of information about this study (eg, objectives, study design) is given to help the reader's interpretation.

This SAP must be finalized prior to the lock of the clinical database. Additionally, the SAP and TFL shells should be finalized prior to any programming activities commencing.

This SAP supersedes any statistical considerations identified in the protocol; where considerations are substantially different, they will be so identified. If additional analyses are required to supplement the planned analyses described in this SAP, they may be performed and will be identified accordingly in the CSR. Any substantial deviations from this SAP will be agreed with Amgen Inc. and identified in the CSR.

This SAP is written with consideration of the recommendations outlined in the International Conference on Harmonisation (ICH) E3 guideline *Structure and Content of Clinical Study Reports*, ICH E8 guideline *General Considerations for Clinical Trials*, ICH E9 guideline *Statistical Principles for Clinical Trials*.^{1,2,3}

The document history is presented in Appendix 1.

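### Does the variable `pkday` in the BY statement of the example SAS code stop the primary mixed model from producing the rosuvastatin test/reference ratio?

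*SAP*

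**What the plan says.** SAP 8.5.3 sets out the primary analysis in words and then in code. In words, the log-transformed rosuvastatin parameters go into a mixed model: "The model will include treatment as fixed effect and subject as a random effect". AUClast, AUCinf and Cmax are each analysed on their own. For each, the output is a test-minus-reference difference in least squares means with a 90% confidence interval, back-transformed to a ratio. The section continues: "Additionally, the pooled estimate (across all treatments) of the within-subject CV will be calculated". Protocol 8.3 describes the same model: "The model assumes fixed effect for treatment and a random effect for subject".

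The code is introduced with "Examples of the SAS code that will be used are as follows". Its BY statement reads "by parcatln parcatl pkday paramn param". The variable `pkday` appears nowhere else in either document.

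Two other places bear on its meaning. SAP 8.5.1 derives parameters "from the plasma concentrations of rosuvastatin on Days 1 and 6 and sotorasib on Day 6", which labels the rosuvastatin profiles by study day. Protocol 5.6 states: "The study has a fixed treatment sequence".

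**The concern.** A BY statement fits a separate model in each group. The text splits the analysis by PK parameter only, while the code also splits it by `pkday`. The name suggests the study day of the PK profile, and for rosuvastatin the SAP uses only Days 1 and 6. Every subject takes the reference on Day 1 and the test on Day 6, so a split by day is also a split by treatment. The comparison that the model exists to make would then disappear.

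On that reading, the only code printed for the primary analysis cannot deliver the three things its own section promises: the geometric mean ratio, its 90% interval and the pooled within-subject CV. The SAP also says that "the SAP and TFL shells should be finalized prior to any programming activities commencing". It can therefore look as though the primary-analysis code would have to be altered after that point.

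**Working it through.** The plan states no figure to reproduce. The question is whether the contrast can be estimated, so no assumption about variability or effect size is needed.

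**Inputs**
- 3 primary rosuvastatin parameters (SAP 3 and 8.5.3).
- 2 rosuvastatin profiles per subject: reference on Day 1, test on Day 6 (SAP 4).
- 12 completers planned, about 14 enrolled (SAP 4 and 5).
- Treatment numbers 1 (reference) and 2 (test), assumed to follow the order in SAP 6, Table 1.

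**Reading A: `pkday` is 1 or 6**
- BY groups: 3 parameters × 2 days = 6.
- Each group has one treatment and one record per subject, so 12 records.
- With columns (intercept, treatment 1, treatment 2), every row in a Day 1 group is (1, 1, 0) and every row in a Day 6 group is (1, 0, 1). The rank is 1. The contrast test minus reference is (0, −1, 1), which is not a multiple of either row, so it is not estimable.
- Within-subject degrees of freedom = records − rank of [treatment, subject] = 12 − 12 = 0. With 14 subjects, 14 − 14 = 0. Subject and residual variance cannot be separated, so there is no within-subject CV.

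**Reading B: `pkday` is absent, or has one value for both rosuvastatin profiles**
- BY groups: 3, one per parameter.
- Each group has 12 × 2 = 24 records and both treatments.
- (1, 0, 1) − (1, 1, 0) = (0, −1, 1), so the contrast is estimable.
- Within-subject degrees of freedom = 24 − (12 + 1) = 11. With 14 complete subjects, 28 − (14 + 1) = 13.

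| | BY groups | Records per group (n = 12) | Treatments per group | Within-subject df, n = 12 | Within-subject df, n = 14 |
|---|---|---|---|---|---|
| Reading A | 6 | 12 | 1 | 0 | 0 |
| Reading B | 3 | 24 | 2 | 11 | 13 |

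**Which reading do the documents support?** They do not settle it. The ADaM specifications that would fix the coding are not among them. SAP 8.5.1 labels the profiles by day, but SAP 6 labels them by treatment and SAP 8.5.1.4 refers to a second treatment period, so day is not the only label in use. The rest of the code points to Reading B. Treatment is in both the CLASS and MODEL statements, the LSMEANS statement asks for a comparison with treatment 1, and a data set of differences is requested. None of these has a purpose if each group contains one treatment.

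**What happens if Reading A is what gets programmed?** The differences are missing for all three parameters. There is no number that could be mistaken for the ratio, and the programmer is sent back to the text, which leaves only one model to fit.

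**The case for a change.** The best case for acting is that `pkday` has no useful role here. The only inferential comparison is rosuvastatin with and without sotorasib, on three parameters. No planned inference needs a split by day, so the variable either breaks the comparison or does nothing. Deleting it is safe on both readings, while keeping it is safe only under a definition that the SAP omits. The lead-in also describes this as code that will be used, in a document that overrides the protocol's statistical section.

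The point about redundancy stands: the variable is undefined, and the section would read more cleanly without it. The claimed consequence does not stand. The lead-in calls the block an example, and its data set names are unfilled placeholders, so it cannot run as printed and must be adapted in any case. The sentence in SAP 1 about finalising before programming covers the SAP and the TFL shells; it does not freeze program code. The same section asks for agreement and reporting only of substantial deviations from the SAP. Removing a grouping variable so that the program matches the SAP's own prose is not such a deviation.

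**Conclusion.** The concern is right on its stated condition and changes nothing. If `pkday` is the study day, the example code loses the treatment contrast and all 11 within-subject degrees of freedom (13 with 14 complete subjects). If it is constant across the two rosuvastatin profiles, the output is as intended. In either case the governing text in SAP 8.5.3 and Protocol 8.3 is correct, complete and consistent. It leaves no choice open that could be made after seeing the data. A failure would be obvious at the first run and put right by following that text.

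This is a clerical matter in sample code. It has no effect on design, data, estimand, ratio or interval. The conclusion rests on two assumptions: that the analysts treat the prose as the specification and the code as illustration, and that missing treatment differences in the primary analysis would be noticed. Both are safe.

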8.6. Safety and Tolerability Assessments

8.6.1. Adverse Events

All AEs will be coded using the Medical Dictionary for Regulatory Activities (MedDRA) Version 24.0 (or higher if a new version is issued during the study; see the DMP for more details). All AEs will be assigned a severity grade using Common Terminology Criteria for Adverse Events (CTCAE) Version 5.0 (or higher if a new version is issued during the study; see the protocol for more details).

A treatment-emergent adverse event (TEAE) will be defined as an AE that starts during or after dosing, or starts prior to dosing and increases in severity after dosing.

A treatment-related TEAE will be defined as a TEAE with a relationship related to the study treatment, as determined by the investigator.

All AEs will be listed. In addition to the data recorded in the database, the listings will include derived onset time and duration. Onset time will be calculated from the time of dosing for TEAEs only.

CONFIDENTIAL

The frequency of subjects with TEAEs and the number of TEAEs will be summarized for the following categories:

- TEAEs (overall, serious, leading to discontinuation, and leading to death) by treatment
- TEAEs by severity and treatment
- Treatment-related TEAEs (overall, serious, leading to discontinuation, and leading to death) by treatment
- Treatment-related TEAEs by severity and treatment

The frequency of subjects will be summarized separately for TEAEs and treatment-related TEAEs by the following:

- System organ class, preferred term, and treatment
- Preferred term and treatment

For the AE data the following rules will apply:

- For the derivation of treatment-emergent status (applicable to all AEs): If the start date/time of an AE is incomplete or missing, an AE will be assumed to not be a TEAE, unless the incomplete start date/time or the end date/time indicates an AE started after dosing.
- For the derivation of treatment-related status (applicable to TEAEs only): If the study treatment relationship for a TEAE is missing, a TEAE will be assumed to not be a treatment-related TEAE.
- For the derivation of onset time (applicable to TEAEs only): If the start date/time of a TEAE is missing, onset time will not be calculated. If the start date/time of a TEAE is incomplete, where possible, the minimum possible onset time will be calculated and presented in '≥DD:HH:MM' format (eg, if the date/time of dosing is 01MAY2019/08:00 and recorded start date/time of a TEAE is 03MAY2019, then the minimum possible onset time will be calculated by assuming a TEAE started at the first hour and minute of 03MAY2019 [03MAY2019/00:00], thus will be presented as onset time ≥01:16:00 in the listing). If the start date of a TEAE is the same as the date of dosing but the start time of a TEAE is missing, an onset time will be presented as '≥00:00:01'. Any clock changes will be accounted for in the derivation.
- For the derivation of duration (applicable to all AEs): If the end date/time of an AE is missing, duration will not be calculated. If the start or end date/time of an AE is incomplete, where possible, the maximum possible duration will be calculated and presented in '≤DD:HH:MM' format (eg, if the start of an AE date/time is 01MAY2019/08:00 and its recorded end date/time is 03MAY2019, then the maximum possible duration will be calculated by assuming an AE ended at the last hour and minute of 03MAY2019 [03MAY2019/23:59], thus will be presented as

Page 18 of 23

duration ≤02:15:59 in the listing). Any clock changes will be accounted for in the derivation.

- For the calculation of TEAE summary statistics: If the severity of a TEAE is missing, that TEAE will be counted under the 'missing' category.
- For the calculation of TEAE summary statistics: If a subject experienced multiple TEAEs with the same preferred term for the same treatment, this will be counted as 1 TEAE for that treatment under the maximum severity recorded.

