- The Investigator will attempt to establish a diagnosis of the event based on signs, symptoms, and/or other clinical information. In such cases, the diagnosis (not the individual signs/symptoms) will be documented as the adverse event/serious adverse event.

Evaluating Adverse Events and Serious Adverse Events

Assessment of Severity

The Investigator will make an assessment of severity for each adverse event and serious adverse event reported during the study. The assessment of severity will be based on the Common Terminology Criteria for Adverse Events (CTCAE) grading scale. For the CTCAE grading scale version 5.0 or higher, refer to:
https://ctep.cancer.gov/protocolDevelopment/electronic_applications/ctc.htm.

Assessment of Causality

- The Investigator is obligated to assess the relationship between investigational product(s), protocol-required therapy, and/or study-mandated procedure and each occurrence of each adverse event/serious adverse event.
- Relatedness means that there are facts or reasons to support a relationship between investigational product and the event.
- The Investigator will use clinical judgment to determine the relationship.
- Alternative causes, such as underlying disease(s), concomitant therapy, and other risk factors, as well as the temporal relationship of the event to study treatment administration will be considered and investigated.
- The Investigator will also consult the Investigator's Brochure and/or Product Information, for marketed products, in his/her assessment.
- For each adverse event/serious adverse event, the Investigator must document in the medical notes that he/she has reviewed the adverse event/serious adverse event and has provided an assessment of causality.
- There may be situations in which a serious adverse event has occurred and the Investigator has minimal information to include in the initial report. However, it is very important that the Investigator always make an assessment of causality for every event before the initial transmission of the serious adverse event data.
- The Investigator may change his/her opinion of causality in light of follow-up information and send a serious adverse event follow-up report with the updated causality assessment.
- The causality assessment is 1 of the criteria used when determining regulatory reporting requirements.

Follow-up of Adverse Event and Serious Adverse Event

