8.1.2. Calculation of the Summary Statistics

For continuous data the following rules will be applied:

• Missing values will not be imputed, unless specifically stated otherwise.

- Unrounded data will be used in the calculation of summary statistics.
- If the number of subjects with valid observations (n) <3, summary statistics will not be calculated, with the exception of n, minimum, and maximum.
- In general, as early termination data are not associated with any scheduled timepoint, they will be excluded from all calculations of summary statistics and statistical analyses. Exceptions may be made where justified.

For categorical data the following rules will be applied:

- For ordered categorical data (eg, AE severity), all categories between the possible minimum and maximum categories will be included, even if n = 0 for a given category.
- For non-ordered categorical data (eg, race), only those categories for which there is at least 1 subject represented will be included; unless specifically stated otherwise.
- Missing values will not be imputed, unless specifically stated otherwise. A 'missing' category will be included for any parameter for which information is missing. This will ensure that the population size totals are consistent across different parameters.

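### SAP 8.6.1 counts a TEAE with missing relationship as not treatment-related: a permitted but unexplained and anti-conservative exception, unlike the handling of missing severity

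*SAP*

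**What the plan says.** The rule is in the list of AE conventions in SAP 8.6.1: "If the study treatment relationship for a TEAE is missing, a TEAE will be assumed to not be a treatment-related TEAE". The same section defines the concept by the investigator's judgement: "A treatment-related TEAE will be defined as a TEAE with a relationship related to the study treatment, as determined by the investigator".

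The flag derived from this rule decides which events enter the treatment-related outputs. These are the overview (overall, serious, leading to discontinuation, leading to death), the tables by system organ class and preferred term, and the table listed as "Treatment-related TEAEs by severity and treatment".

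Two other SAP rules cover missing categorical data:

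- Severity, also in 8.6.1: "If the severity of a TEAE is missing, that TEAE will be counted under the 'missing' category".
- The general rules in 8.1.2: "Missing values will not be imputed, unless specifically stated otherwise", and "A 'missing' category will be included for any parameter for which information is missing".

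Protocol Appendix 1 makes causality assessment compulsory: "The Investigator is obligated to assess the relationship between investigational product(s), protocol-required therapy", for each occurrence of each event. On the output side, SAP 8.6.1 states: "All AEs will be listed".

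**The concern.** Two attributes of the same adverse event are handled differently when they are missing. An absent severity grade is shown as absent. An absent relationship is turned into a negative answer, and the SAP gives no reason. The negative answer is also the favourable one, so any gap in the data works toward fewer treatment-related events.

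The safety and tolerability of the combination, and of rosuvastatin alone, are a secondary objective, and the treatment-related tables are one of the main ways it is reported. With about 14 subjects, a single subject is a visible share of the denominator. As planned, those tables carry no count or footnote of events left out because nobody recorded a relationship.

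**Working it through.** The documents state no figure on this point, so there is none to reproduce. The check compares the rules, then shows how large one affected subject would be.

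**1. The rules side by side**

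| Missing item | Handling | Place |
|---|---|---|
| Any categorical value | Not imputed unless stated otherwise; 'missing' category shown | SAP 8.1.2 |
| TEAE severity | 'Missing' category | SAP 8.6.1 |
| TEAE relationship | Set to not related; no category, count or footnote | SAP 8.6.1 |

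The relationship rule is a stated exception, which 8.1.2 permits. It is the odd one out of the three.

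**2. Direction.** Compare the planned result with what full assessment would have given. If the unassessed event would have been judged unrelated, the rule gives the same count. If it would have been judged related, the event is lost from the related count. The subject is lost too, unless he or she has another related TEAE on that treatment. No case raises the number of related events or of subjects with one. In the by-severity table, a subject can also drop to a lower grade if the unassessed event was the more severe of two with the same preferred term.

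**3. Size of one affected subject.** Inputs: about 14 subjects enrolled so that about 12 complete (Protocol 8.1, SAP 5). For k subjects whose only related TEAE on that treatment lacks a relationship, the change in incidence is k/n:

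- k = 1: 1/14 = 7.1 points; 1/12 = 8.3 points.
- k = 2: 2/14 = 14.3 points; 2/12 = 16.7 points.

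**4. Illustration under assumed missing rates.** The documents give neither a missing rate m nor an expected number of related subjects. Assume 4 of 14 subjects truly have a related TEAE (28.6%), one each, with assessments missing independently. Expected reported incidence = (4/14)(1 − m). The chance of losing at least one related subject = 1 − (1 − m)^4.

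| m (assumed) | Expected reported incidence | Chance of losing at least one |
|---|---|---|
| 0% | 28.6% | 0 |
| 5% | 27.1% | 0.19 |
| 10% | 25.7% | 0.34 |
| 20% | 22.9% | 0.59 |

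With 4 of 12 (33.3%), the expected reported incidences are 33.3%, 31.7%, 30.0% and 26.7%. These figures show sensitivity only. They do not predict this trial.

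**The case against.** The case for leaving the rule alone is respectable, and much of it stands.

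- **The exception is permitted.** A reader might infer that the sentence contradicts the general no-imputation rule. It does not, because 8.1.2 yields to anything specifically stated and 8.6.1 states it. SAP 8.1.1 also rules out imputation, but only for mitigating actions after COVID-19-related deviations.
- **The definition points the same way.** Relatedness is what the investigator determined. With no determination, the event does not meet the definition, so the rule partly restates it. Severity is a set of rows in which a 'missing' row fits naturally, whereas relatedness is an inclusion flag. This weakens the analogy, but it does not explain why unassessed events should go uncounted.
- **Nothing is reported as judged unrelated.** A reader might infer that unassessed events are presented as assessed and unrelated. No table of unrelated events is planned. The event is simply absent from the related subset and stays in every all-TEAE table.
- **The handling is not hidden.** The rule is written in the SAP, all AEs are listed with the recorded data, and a blank relationship can be found in a listing this small. What is lacking is a count in the table.
- **Missing values should be rare.** Assessment is mandatory under Protocol Appendix 1, and for a serious event it must precede the first report. Subjects are confined from Day -1 to Day 11, and the investigator resolves queries and signs the eCRF (Appendix 6). Against this, SAP 8.1.1 itself names incomplete data entry and unanswered queries as risks.

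A further tempting reading is that relationship to rosuvastatin might be missing systematically. The attribute list in Appendix 1 refers to investigational product(s) and study-mandated procedures, while rosuvastatin is the non-investigational product. But the causality text in the same appendix covers protocol-required therapy, and the eCRF is not among the documents. They do not support that inference.

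**Conclusion.** The point holds as a minor one. The rule is legitimate in form, but unexplained, anti-conservative and out of line with the treatment of missing severity. Its effect depends on at least one relationship still being missing at database lock. If none is, no result changes.

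The change of 7.1 points (n = 14) or 8.3 points (n = 12) applies to a subject with no other related TEAE on that treatment whose unassessed event would have been judged related. If the event would have been judged unrelated, the planned count is already right, so the rule does not guarantee understatement. The number of such subjects cannot be derived from the documents, and mandatory assessment suggests that it is small. Safety is summarised without inferential analysis (SAP 8.6.6), and the primary PK analysis is untouched.

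**What to change.** Replace the sentence in SAP 8.6.1 with wording such as: *If the relationship of a TEAE to study treatment is still missing after query, the event will be shown in a separate 'relationship missing' row or count in each treatment-related summary.* This follows the SAP's own approach to severity and puts no answer in the investigator's place.

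An acceptable alternative is to count such an event as treatment-related and footnote the number so imputed. That is the cautious direction, but it is still an imputation, and the documents do not require it.

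The cost is one SAP sentence, one programming flag, and an extra row or footnote. The separate row has no statistical downside. The alternative may slightly overstate related events.
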